10.7.3 Participant reported secondary efficacy endpoints

Participant reported secondary efficacy endpoints are:

- Time from TV1 to clinically significant pain reduction measured using a Visual Analogue Scale (VAS) instrument. For the purpose of this protocol a clinically significant reduction of pain is a mean reduction of ≥ 20.65 mm or a mean decrease of $\geq 10-20\%$ in pain as measured on a 0-100 mm VAS (23; 24).
- Time from TV1 to first instance of no study ulcer pain measured using VAS.

(No pain = < 5 mm on VAS when VAS scores: 0-4 mm = no pain; 5-44 mm = mild pain; 45-74 mm = moderate pain; and 75-100 mm = severe pain) (1).

- Pain score at EOT measured using VAS.
- Change from TV1 in QoL at EOT assessed using the CWIS.
- Change from TV1 in QoL at EOT assessed using EQ-5D-5L.

10.7.4 Safety Assessments

Safety will be assessed using the following parameters:

- Incidence of AEs

- Incidence of SAEs
- Incidence of study ulcer infection
- Incidence of study treatment related AEs (including geko™, compression bandaging and any dressings used to treat the study wound)
- Incidence of investigational device (geko™) related AEs
- Pain in the ulcer site (sudden onset of pain or increase in pain during the study Treatment Phase)

10.8 Participant Disposition

The disposition of all patients who sign an informed consent form (ICF) will be provided. The numbers of patients screened, randomised, completed, and discontinued during the study, as well as the reasons for all post-randomisation discontinuations will be summarised by treatment group, for all centres combined and each centre separately. Disposition and reason for study discontinuation will also be provided as a by-participant listing.

10.9 Demographic and Baseline Characteristics

Demographics and baseline characteristics will be summarised by treatment group using appropriate descriptive statistics.

10.10 Analysis Populations

10.10.1 Intent to Treat Population

The Intent-to-Treat (ITT) population is defined as the set of randomised participants who have at least one post-randomisation efficacy assessment for wound healing. The ITT population will be the primary population for the analysis of primary and secondary endpoints.

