Indication for Use: Indicated for use as an adjunct to Standard Care (SC) in the treatment of Venous Leg Ulcers (VLUs)	
Objective: The objective of this study is to compare the efficacy of a daily geko™ device treatment duration of 12 hours, in conjunction with SC, to SC alone, in patients with venous leg ulcers.	
Endpoints: Primary Efficacy The primary efficacy endpoint is linear healing rate (LHR) of the study ulcer from first Treatment Phase visit (TV1) to the End of Treatment (EOT) as compared with LHR from first Run-in Phase visit (RV1) to TV1. 
• EOT is defined as Treatment Phase visit 5 (TV5), withdrawal or that Treatment Phase visit at which 100% re-epithelialisation without drainage is first determined by the Principal Investigator (PI) or designee, whichever comes first. Each participant will be used as his/her own control. Wound area will be measured by a blinded independent wound expert using digital images taken at RV1, TV1 and at EOT. “Healing” of the study ulcer is determined by the PI or designee. “Healing” is defined as 100% re-epithelialised without drainage as confirmed at the Healing Confirmation visit (HCV).	

Name of Sponsor/Company: Firstkind Ltd, [name]	
Name of Study Product: geko™ neuromuscular stimulator	
Comparator Product: Multilayer, multicomponent compression therapy intended for the treatment of VLU (Standard Care)	
Protocol Number: FSK-VLU- 004	Indication: Venous Leg Ulcers (VLUs)

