2.1.2 Secondary Efficacy Endpoints

The secondary efficacy endpoints are:

- Weekly LHR measured by an independent blinded wound expert using digital images taken at each weekly visit until TV5, withdrawal or healing whichever comes sooner.
- Wound healing status at baseline and EOT assessed by an independent blinded wound expert using PWAT to evaluate digital images taken at RV1, TV1 and at withdrawal, healing or at the end of the Treatment Phase (TV5), whichever comes sooner.
- Incidence of healing at EOT, as determined by the Investigator

“Healing” of the study ulcer is determined by the PI or designee. “Healing” is defined as 100% re-epithelialised without drainage as confirmed at the Healing Confirmation visit (HCV).

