4.4 Follow-up Phase

Participants who completed TV5 will be contacted after 4, 8 & 12 weeks to find out the status of the study wound.

At week 13, 17 and 21; a member of the research team (at the clinical site) will contact the patient to find out

- whether the wound is healed or not healed
- if healed (the date wound was healed)

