10.7.2 Secondary Efficacy Endpoints

The secondary efficacy endpoints are:

- Weekly LHR measured by an independent blinded wound expert using digital images taken at each weekly visit until EOT.
- Wound healing status at baseline and EOT assessed by an independent blinded wound expert using PWAT to evaluate digital images taken at RV1, TV1, EOS, and at HCV, if scheduled.
- Incidence of healing at end of study, as determined by the Investigator

"Healing" of the study ulcer is determined by the PI or designee. "Healing" is defined as 100% re-epithelialised without drainage as confirmed at the Healing Confirmation visit (HCV).

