10.11 Treatment Failures

Participants who are withdrawn or discontinue during the Treatment Phase and/or who do not achieve healing during the Treatment Phase will not be replaced and will be considered treatment failures.

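### Incidence of healing is analysed in a restricted 'ITT' set, so participants lost after randomisation with no later assessment are failures under 10.11 but missing from the denominator

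*Combined protocol and SAP*

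**What the plan says.** **Analysis set.** Section 10.10.1, repeated in the synopsis, defines the ITT population as "the set of randomised participants who have at least one post-randomisation efficacy assessment for wound healing". It adds: "The ITT population will be the primary population for the analysis of primary and secondary endpoints". Incidence of healing is one of those secondary endpoints, and section 10.12.1 compares it between groups with Fisher's exact test.

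**Failure rule.** Section 10.11 covers "Participants who are withdrawn or discontinue during the Treatment Phase", together with those who do not heal in that phase, and says they "will not be replaced and will be considered treatment failures". It does not require a post-randomisation assessment.

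**Withdrawal visit.** Section 5.2 says that participants who meet the premature-withdrawal criteria in the Treatment Phase have the TV5 assessments done. These include the investigator's healing assessment. The same section also foresees participants who are lost to follow-up.

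**Time point.** Section 2.1.2 lists "Incidence of healing at EOT, as determined by the Investigator", and the synopsis also uses EOT. Section 10.7.2 lists "Incidence of healing at end of study, as determined by the Investigator". The synopsis defines EOT ("EOT is defined as Treatment Phase visit 5 (TV5), withdrawal or that Treatment Phase visit at which 100% re-epithelialisation without drainage is first determined", whichever comes first). The protocol does not define end of study.

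**The concern.** A restricted set is defensible for LHR, because a treatment-phase slope cannot be computed without a later image. Incidence of healing is different: it is binary, and the protocol already has a rule for those who leave. Nothing says whether 10.10.1 or 10.11 governs its denominator.

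Everyone removed by 10.10.1 is, by construction, not known to have healed. Removing them can only raise the rate in their arm. If the number removed differs between arms, the comparison is shifted by something other than treatment. Unequal early loss is plausible: only the wound expert who reads the images is blinded, only one arm wears a device, and the PI or designee judges healing. The documents do not show that it happens.

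The two names for the time point are a smaller matter. They leave the endpoint's wording inconsistent between sections but affect both arms alike.

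**Working it through.** **No stated figure to reproduce for this endpoint.** The protocol gives no expected rate, power or sample size for incidence of healing. Its current calculation (section 10.5.2, 25 subjects) is for the paired LHR comparison. There, 0.58/0.97 = 0.598; at two-sided 0.05, n = 24 gives 80.1% power and n = 25 gives 81.8%. That figure reproduces to within one participant, but it says nothing about healing.

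**Who is dropped**

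| Participant after randomisation at TV1 | 10.11 | 10.10.1 set |
|---|---|---|
| Leaves in week 1, attends the withdrawal (TV5) assessments | Failure | Included |
| Attends TV2, leaves later | Failure | Included |
| Lost after TV1, no later assessment of any kind | Failure | **Excluded** |

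Table 2 places the first scheduled healing assessment at TV2, so only the third row is affected.

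**Inputs**
- 60 randomised (section 3.1.1). The allocation ratio is not stated; 30 per arm is an assumption.
- Discontinuation of at most about 20% (section 10.2), so at most 0.20 × 30 = 6 per arm.
- True healing rate by EOT: not given. Rates of 10% to 45% are an assumed range.

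**Inflation within an arm.** With h healed and k unassessed failures dropped, the rate moves from h/30 to h/(30 − k), a factor of 30/(30 − k).

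| k | Factor | 20% (6/30) becomes |
|---|---|---|
| 1 | 1.03 | 6/29 = 20.7% |
| 2 | 1.07 | 6/28 = 21.4% |
| 3 | 1.11 | 6/27 = 22.2% |
| 6 | 1.25 | 6/24 = 25.0% |

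The last row needs every predicted discontinuation to be unassessed after TV1. It is an upper bound.

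**Spurious difference between arms.** If the true rate p is the same in both arms and only one arm loses k, the expected gap is p × [30/(30 − k) − 1].

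| True rate | 3 vs 0 dropped | 6 vs 0 dropped |
|---|---|---|
| 10% | 1.1 points | 2.5 points |
| 20% | 2.2 | 5.0 |
| 30% | 3.3 | 7.5 |
| 45% | 5.0 | 11.25 |

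With equal loss and equal true rates, both rates rise and no gap is expected.

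**Effect on Fisher's test (two-sided)**
- 8/30 vs 2/30 gives p = 0.080; with one failure dropped from the first arm, 8/29 vs 2/30 gives p = 0.042.
- 9/30 vs 3/30 gives p = 0.104; with three dropped, 9/27 vs 3/30 gives p = 0.0498.
- These are chosen near-threshold cases. Much of the first jump is discreteness: with equal group sizes the two-sided p is twice the one-sided tail (2 × 0.040), and that symmetry goes when one group has 29.
- Type I error at a nominal 0.05 and a true rate of 30% is 2.6% with none dropped, 4.4% with 3 vs 0, and 6.6% with 6 vs 0. At 45% the figures are 2.7%, 5.2% and 10.1%.

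The test is conservative at this size, so at 30% the nominal level is exceeded only near the upper bound. At 45% it is just reached with 3 vs 0.

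**The case against.** The best defence is section 5.2. A participant who stops in week 1 and attends the withdrawal assessments has a post-randomisation healing assessment, enters the ITT set and counts as a failure there. So a reader who infers that the set removes everyone who leaves before TV2 goes too far. Only those with no assessment at all after TV1 are lost, and they may be few. The two rules can also be read together, with 10.11 applied inside the 10.10.1 set. That is a possible reading, but the text does not state it, and under it the unassessed still vanish.

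A reader might also infer that the exclusion favours geko. The documents do not support that: they report no losses by arm, and disappointed standard-care participants could equally be the ones who disappear.

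A third tempting inference is that 'end of study' in 10.7.2 moves the endpoint to the last follow-up contact and so gives a much higher healing rate. That does not fit. The endpoint needs the investigator's determination and confirmation at an HCV, and section 4.3 schedules an HCV only after closure seen at a treatment visit. Section 4.4 ("At week 13, 17 and 21; a member of the research team (at the clinical site) will contact the patient to find out") collects participants' own reports of closure, which are a separate endpoint. Section 9.4 also treats EOT as part of the end-of-study procedures. What stands is an inconsistency of terms.

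Finally, sections 10.1 and 10.12 defer detail to a separate SAP, which may settle the denominator. None of its text is available here, and the protocol's definitions would still need aligning.

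**Conclusion.** The point holds in a limited form. For incidence of healing, participants with no assessment after TV1 are failures under 10.11 and missing under 10.10.1, and the protocol does not say which rule governs. Assuming 30 per arm, the plausible effect is a factor of 1.03 to 1.11 on an arm's rate (one to three dropped); 1.25 is the ceiling. Bias between arms requires unequal unassessed loss, whose existence and direction are unknown. This is one secondary endpoint for which no power is stated, and the restricted set remains reasonable for LHR. Correction is still worthwhile, because one or a few missing failures can move a near-threshold Fisher result and the protocol already contains the rule that resolves it. The time-point mismatch is a consistency edit and favours neither arm.

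**What to change.** 1. In 10.10.1 (and its copy in the synopsis) and 10.12.1, state that incidence of healing is analysed in all randomised participants. The event is HCV-confirmed healing first determined by EOT; unconfirmed or missing counts as not healed.
2. Rename the current ITT set as modified ITT, keep it for LHR, and report by arm how many randomised participants it excludes and why.
3. In 10.7.2, replace 'end of study' and 'EOS' with EOT, to match section 2.1.2 and the synopsis.
4. Carry the same wording into the separate SAP before database lock.

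The cost is a few sentences, with no new data or visits. Reported healing rates may be slightly lower. In the examples above, 20.7% to 22.2% returns to 20%.

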10.10.2 Per Protocol Population

The Per Protocol (PP) population is defined as the set of participants who meet the ITT population requirements, defined above, and who were not associated with a major protocol violation/deviation. This population will be identified before the database lock.

10.10.3 Safety population

The Safety population is defined as any participant receiving treatment after randomisation. This population will be used for the analysis of safety parameters.

10.11 Treatment Failures

Participants who are withdrawn or discontinue during the Treatment Phase and/or who do not achieve healing during the Treatment Phase will not be replaced and will be considered treatment failures.

10.12 Analysis Methods

A SAP will be developed and approved before the database is locked. The SAP will present the detailed statistical methodology to be used in analysing the efficacy and safety data from this study.

All statistical tests will be two-sided and a 0.05% significance level maintained throughout the analyses.

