10.5.1 Procedure for Interim Analysis

The data to be used in the interim analysis and the treatment assignment of each randomised subject will be given to the statistician. Using this data, the independent statistician will calculate the following metrics for the primary end point:

1. Mean and standard deviation of LHR in each group.
2. The dropout rate at the time of the Interim Analysis, IA
3. The statistical power of the trial at the time of the IA (using a conditional power approach).
 - a. If the statistical power is larger than 50%, then the sample size will be adjusted upward and no Type I error rate adjustment will be made to the final analysis.
 - b. If the statistical power is less than 50%, the Type I error rate will be inflated and statistical adjustment will be made to the final analysis if the decision to increase the sample size is made. That is, the observed p-value, as well as the point estimate of the response rates, and the 95% CIs will be based on:

$$p\text{-value} = 2 * \{1 - T_2(n_1+n_2 - 1) (|z_1 + z_2|/\sqrt{2})\},$$

Healing rate for each treatment group: $\hat{S} = (\sqrt{n_1} \times \hat{S}_1 + \sqrt{n_2} \times \hat{S}_2) / (\sqrt{n_1} + \sqrt{n_2})$,

95% Confidence Intervals = $(\hat{S} - 2 \text{ta}/2:2(n_1+n_2 - 1)\sigma, \hat{S} + 2 \text{ta}/2:2(n_1+n_2 - 1)\sigma)$

where n_1 is the sample size in the treatment group before interim analysis and n_2 is the sample size in treatment group after the interim analysis; $T_2(n_1+n_2 - 1)$ (.) is t distribution with $2(n_1+n_2-1)$ degrees of freedom. The \hat{S}_1 is the healing rate of the n_1 observation before the interim analysis and \hat{S}_2 is the healing rate of the n_2 observation after the interim analysis. The $(\sqrt{n_1} + \sqrt{n_2})\sigma$ is the observed pooled standard deviation before and after the interim analysis.

4. Using the observed metrics above, along with Type I Error Rate of 0.05, the sample size will be re-calculated and the independent statistician will provide the following to the sponsor and the statistician responsible for the trial:
 - a. Re-estimation of sample size using the observed rate of healing and dropout rate
 - b. The difference in percentage of healed subjects
 - c. The healing rate in Treatment arms
 - d. The healing rate in the Control arm
 - e. The power used in calculating the new sample size

No other information will be shared with the sponsor or the statistician responsible for this trial.

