10.5.2 Results of Interim Analysis

The new sample size calculation is:

Based on a pair-wise comparison of geko™ 12h run-in vs treatment:

From the interim data, there is a mean difference of 0.58 mm/week between run-in and treatment and a standard deviation of 0.97 mm/week.

Assuming requirements of 80% power and $p=0.05$ (2-sided) 25 subjects would be needed in the geko™ 12H group. (30)

Little benefit is foreseen in continuing the geko™ 6h group, as statistical significance is not expected at the projected number of subjects in this trial.

From the results of the Interim Analysis the new Treatment Groups are:

Group	Description
SC	Standard care (multilayer, multicomponent compression intended for the treatment of VLU)
geko 12h	geko™ version XW, W-3 or variant (12 h daily neuro-stimulation) and SC

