10.12.1 Efficacy Analyses

Primary Endpoint: The primary efficacy endpoint is linear healing rate (LHR) from TV1 to EOT as compared with LHR from RV1 to TV1. LHRs will be measured by a blinded wound expert using digital images at RV1, TV1, and EOT.

Within treatment groups, treatment phase will be compared to run-in phase by paired non-parametric test (Wilcoxon signed rank). Effects will be compared between groups using non-paired non-parametric tests (Mann-Whitney).

Secondary Endpoints:

Weekly LHR shall be compared as above.

EOT healing status between groups shall be compared by Mann-Whitney U test on the PWAT scores. Weekly LHR can be tested using the same method (and same wording) as final LHR. Incidence of healing shall be compared between groups using Fisher's exact test.

Intra-group pain reduction measured on a visual analogue scale (VAS) will be analysed using paired t-test.

Inter group differences in time to clinically significant reduction in VAS shall be tested using Mann-Whitney u-test.

Intra-group changes to both Quality of Life (QoL) instruments in the study (CWIS and EQ-5D-5L) shall be tested using Wilcoxon signed rank test.

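### Section 10.12 sets the significance level at 0.05% (0.0005), while the revised sample size and the interim procedure use 0.05; almost certainly a slip for 5%

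*Combined protocol and SAP*

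**What the plan says.** The only explicit significance level in section 10.12 (Analysis Methods) is this: "All statistical tests will be two-sided and a 0.05% significance level maintained throughout the analyses". It is current body text and covers every test listed in section 10.12.1, including the within-group comparison of the primary endpoint: "Within treatment groups, treatment phase will be compared to run-in phase by paired non-parametric test (Wilcoxon signed rank").

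Elsewhere the protocol states its error rate differently:

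- Section 10.5.2, repeated in the synopsis, gives the revised sample size: "Assuming requirements of 80% power and $p=0.05$ (2-sided) 25 subjects would be needed in the geko™ 12H group". Its inputs are that "there is a mean difference of 0.58 mm/week between run-in and treatment and a standard deviation of 0.97 mm/week".
- Section 10.5.1, step 4, has the independent statistician take the observed metrics "along with Type I Error Rate of 0.05, the sample size will be re-calculated".
- Section 10.5.1, step 3b, prescribes 95% confidence intervals for the adjusted final analysis: "as well as the point estimate of the response rates, and the 95% CIs will be based on".

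Section 10.2, which holds the superseded three-arm calculation, states no significance level. Sections 10.1 and 10.12 leave detailed methods to a separate SAP, to be approved before the database is locked.

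**The concern.** A level of 0.05% is 0.0005, which is 100 times smaller than 0.05. The protocol therefore sizes the trial at one threshold and says it will test at another. No multiplicity adjustment, alpha-spending rule or other reason for 0.0005 appears anywhere.

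The sentence is the written decision rule, so the discrepancy matters even if the intention is easy to guess. If it is followed literally, the geko 12h comparison loses most of the power that its sample size was meant to provide. If it is ignored and 5% is used, the analysis departs from the protocol text, and a correction made after results are known could look like a relaxed criterion. The separate SAP could also inherit the wording.

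**Working it through.** **Inputs**

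- Mean paired difference, run-in versus treatment, geko 12h arm: 0.58 mm/week (section 10.5.2)
- SD: 0.97 mm/week (section 10.5.2)
- Required power: 80% (section 10.5.2)
- Level used for sizing: 0.05, two-sided (section 10.5.2 and synopsis)
- Level stated for testing: 0.05% = 0.0005, two-sided (section 10.12)
- Stated n in the geko 12h arm: 25 (section 10.5.2)
- Total to be randomised: 60 (section 3.1.1)

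The standardised effect is d = 0.58/0.97 = 0.598. Everything below concerns the within-arm paired comparison, because that is what was sized.

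**Step 1. Reproduce the plan's 25 at 0.05.** The normal approximation is n = [(z for 1 − α/2 + z for power) / d]².

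- (1.960 + 0.842)² × (0.97/0.58)² = 21.95, so 22.
- Adding the small-sample correction z²/2 = 1.96²/2 = 1.92 gives 23.9, so 24.
- The exact paired t-test (noncentral t) also needs 24, with power 80.1%.
- Dividing 24 by 0.955, the asymptotic efficiency of the Wilcoxon test relative to the t-test, gives 25.1.

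The stated 25 is therefore consistent with a two-sided 0.05.

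**Step 2. Repeat at 0.0005.** The z value rises from 1.960 to 3.481.

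- (3.481 + 0.842)² × (0.97/0.58)² = 52.3, so 53.
- With the correction 3.481²/2 = 6.06: 58.3, so 59.
- Exact paired t: 59 (power 80.8%; 58 gives 79.7%).

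The stated 25 cannot be obtained at 0.0005.

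**Step 3. Power at each level.** For the paired t-test, the noncentrality is d√n with n − 1 degrees of freedom; at n = 25 it is 0.598 × 5 = 2.99. The Wilcoxon signed-rank figures come from 200,000 simulations with exact critical values, assuming normally distributed differences.

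| n in geko 12h arm | Test | Power at 0.05 | Power at 0.0005 |
|---|---|---|---|
| 25 | Paired t | 81.8% | 19.6% |
| 25 | Wilcoxon | 79.7% | 18.5% |
| 30 | Paired t | 88.6% | 29.4% |
| 30 | Wilcoxon | 87.3% | 27.3% |

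The n = 30 rows assume that the 60 participants are split equally; no allocation ratio is stated. With the Wilcoxon test at 0.0005, n = 60 gives 79.9% and n = 61 gives 81.0%, so about 61 would be needed for 80% power.

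**Step 4. What result would count as significant (paired t-test, n = 25, SD 0.97).** The standard error is 0.97/√25 = 0.194 mm/week.

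- At 0.05: 2.064 × 0.194 = 0.400 mm/week.
- At 0.0005: 4.021 × 0.194 = 0.780 mm/week, above the planned 0.58.
- A result exactly at the planning values gives t = 0.58/0.194 = 2.99 on 24 degrees of freedom, two-sided p = 0.0064. It is significant at 0.05 and not at 0.0005.

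**The case against.** The strongest reply is that this is an obvious typographical slip. Section 10.5.2 and the synopsis both state a two-sided 0.05 outright, no statistician is likely to test at 0.0005, and the SAP may already say 5%. On that view the matter is editorial, and the power figures describe a scenario that nobody intends.

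Much of this stands. The intended level can be recovered from the document, and the fall from 82% to 20% is not an expected loss of power. Its main use is to show that 25 fits 0.05 and does not fit 0.0005. The 95% intervals in section 10.5.1 are also weaker evidence than the rest: they belong to a branch that applies only if power is below 50% and the sample size is increased, and a 95% interval can be reported beside a stricter test. They corroborate 5% but do not by themselves contradict section 10.12. The 0.05 in step 4 of that section governs the sample size re-calculation, not the final tests.

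The objection does not remove the problem. Section 10.12 defers detail to the SAP but states the level itself, so a SAP at 5% would then conflict with the protocol. Results between the two thresholds are plausible, since the planning values themselves fall there. An obvious intention makes the correction easy but does not make the sentence right.

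**Conclusion.** The concern holds. The significance level in section 10.12 is wrong as written, by a factor of 100, and 5% is almost certainly what was meant. Intent cannot be proved from the documents, but every other statement of error rate points to 0.05, and so does the arithmetic behind the 25.

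This is an inconsistency that should be corrected, not a defect in the design. The loss of power arises only under literal application. The calculations rest on the plan's 0.58 and 0.97 mm/week, on normally distributed differences, and on the within-arm comparison alone. The conclusion is the same for the paired t-test and the planned Wilcoxon test, and for 25 or an assumed 30 in the geko 12h arm.

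**What to change.** In section 10.12, replace the 0.05% level with a 5% significance level (alpha = 0.05). The sentence already says that the tests are two-sided, so that need not be repeated. Before database lock, check that the separate SAP states the same level; it is not among the documents reviewed, so its wording could not be confirmed.

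The cost is one phrase and one check. The sample size, the tests and the conduct of the trial are unaffected. The correction should be made and dated before lock, so that it is plainly editorial.
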